#### **SECONDARY OUTCOMES**

- Change in insulin resistance from baseline on POD 2 and POD 3 measured using a technique called HOMA, which utilises serial fasting blood glucose and insulin measurements.
- Stress response following surgery, measured by sampling cortisol levels preoperatively, at the end of surgery, and at 24 hours post-operatively and the inflammatory response measured by CRP levels preoperatively, and on POD 1,2 and 3.
- Ultrasound measurement of gastric volume pre-operatively (see Appendices for technique)
- Recovery profile including:
  - PQRS (see Appendices) score measured pre-operatively, at 2 hours after surgery, POD 3 and POD 7;
  - Muscle strength measured using a grip strength dynamometer pre-operatively, twice daily (morning and afternoon) on POD 1, 2 and 3, and then once daily on alternate days thereafter until discharge (the patient's dominant hand will be used for this measurement, and the best out of three consecutive strengths will be used with mean values analysed);
  - Time to surgical fitness for discharge (see Appendices for criteria) measured in hours (date and time of fitness for surgical discharge is recorded in the ERP database).
- Morbidity measured using the POMS score on POD 2 and POD 5 (see Appendices).
- PONV VAS score on POD 1.
- Sensations of thirst & hunger VAS score immediately pre-operatively and on POD 1.
- Caloric intake POD 1 and 2.
- Ambulation time POD 1 and 2.
- Adverse events i.e. aspiration and hypo- or hyperglycaemia (these are the only relevant safety assessments for these interventions) will be assessed on the operative day for the former & up to the end of POD 1 for the latter.
- Cost analysis: difference in cost between doses of Pre-Load & Generation UCAN and costs of respective hospital and critical care lengths of stay.

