#### 7.3 STATISTICAL METHODS

#### STATISTICAL METHODS FOR ANALYSING PRIMARY AND SECONDARY OUTCOMES

Baseline demographic and clinical variables will be reported for the two groups using summary statistics. Categorical variables will be reported using frequencies and percentages. Quantitative variables will be reported using either the mean and standard deviation or the median and interquartile range depending on the skewness of the data

In terms of the primary outcome, the mean difference in change of insulin resistance from baseline to POD 1 will be compared using either the Independent Samples T-Test or Mann-Whitney U Test. This will depend on the skewness of the data distribution.

Between-group comparisons of quantitative secondary outcomes including change of insulin resistance from baseline to POD 3, the PQRS score and time to surgical fitness will made using either the Independent Samples T-Test or Mann-Whitney U Test, depending on the skewness of the distribution of the data. Categorical secondary outcomes will be compared between groups using the Chi-square test.

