## METHODS FOR ANY ADDITIONAL ANALYSES (EG, SUBGROUP AND ADJUSTED ANALYSES)

If differences are observed in baseline demographic and/or clinical variables prognostic of outcome, then the analysis of the primary and secondary outcomes will be adjusted for using regression-based analysis appropriate to the type of outcome variable. The trial statistician will describe details of sub-group analysis in the statistical analysis plan if possible.

DEFINITION OF ANALYSIS POPULATION RELATING TO PROTOCOL NON-ADHERENCE (E.G., AS RANDOMISED ANALYSIS), AND ANY STATISTICAL METHODS TO HANDLE MISSING DATA (EG, MULTIPLE IMPUTATION) All analysis will be performed according to the intention to treat principle. The primary analysis will be based only on data obtained; sensitivity analysis will explore sensitivity to assumptions around missing data and details will be included in the statistical analysis plan devised by the trial statistician.

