#### WITHDRAWAL OF A PATIENT

In consenting to the trial, patients are consenting to the trial intervention they are allocated, assessments, and data collection. However, patients can withdraw from the SuperStarch Study at any time during the trial. If a patient explicitly states that they no longer wish to take part or contribute further data to the trial, their decision must be respected. The patient's withdrawal from the trial should be recorded in the patient's medical notes and no further data collected. All data collected up to the point of withdrawal will be included in the trial analysis. However, if a patient withdraws consent for any of their data to be used, these will be confidentially destroyed immediately. If a patient is randomised and later found to be ineligible, or the responsible clinician feels that it is no longer appropriate for the patient to continue taking part, then they will be withdrawn from the study and the reason for withdrawal indicated in the medical notes. Patients withdrawn will not be replaced.

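### Time to surgical fitness is compared on observed times only, so a patient who dies or is withdrawn before becoming fit drops out of the main comparison

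*Protocol*

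**What the plan says.** Section 5.4 lists, under the recovery profile among the secondary outcomes, "Time to surgical fitness for discharge (see Appendices for criteria) measured in hours". The appendix on discharge criteria gives five conditions for being fit.

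Section 7.3 assigns the test, with skewness deciding between the two options: "the PQRS score and time to surgical fitness will made using either the Independent Samples T-Test or Mann-Whitney U Test".

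On the analysis set and missing data, Section 7.3 states "All analysis will be performed according to the intention to treat principle", then "The primary analysis will be based only on data obtained", and continues "sensitivity analysis will explore sensitivity to assumptions around missing data and details will be included in the statistical analysis plan".

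Section 9.3, on withdrawal, states "The patient's withdrawal from the trial should be recorded in the patient's medical notes and no further data collected". Data gathered before that point stay in the analysis unless the patient withdraws consent for their use. Withdrawal can also be started by the clinical team, when "the responsible clinician feels that it is no longer appropriate for the patient to continue taking part". Withdrawn patients are not replaced.

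No section says how a patient who dies or leaves the trial before becoming fit enters the comparison of times.

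**The concern.** Time to fitness is the time to an event that some patients may not reach under observation. Neither named test can be computed for a patient without a value, and the observed-data rule supplies none. Such a patient is left out.

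For a death before fitness this is the wrong treatment. It is the clearest failure to recover, yet it would not count against its arm. A withdrawal prompted by a poor post-operative course raises a similar problem: a long, incomplete recovery is removed and the shorter ones stay. This sits badly with the intention-to-treat statement in the same section. It also sits badly with the promise in Section 9.3 to use data collected before withdrawal, because the hours already spent unfit cannot enter either test.

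At stake is the direction of one recovery result in a trial with 20 patients per arm, where one or two patients can move the summary.

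**Working it through.** **The plan's own figure.** No sample size or effect is stated for time to fitness. The only design figure is for the primary outcome (Section 5.6): difference 15%, SD 16%, two-sided 0.05, power 80%, 10% attrition.

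n per arm = 2 × (1.960 + 0.842)² × (16/15)² = 2 × 7.851 × 1.138 ≈ 17.9, so 18. Then 18 / 0.9 = 20, which reproduces the stated 20 per group. The 10% allowance is 0.10 × 20 = 2 patients per arm. It was set for the primary outcome; how many losses would fall between surgery and fitness is unknown.

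**Can a time be missing?** The trial ends when the last patient leaves hospital, so follow-up is not cut off by the calendar. Death or withdrawal before fitness remain as routes to a missing time.

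**Assumed inputs.** The protocol gives no distribution of times and no loss rates. Assumed: two identical arms of 20; log-normal times with median 96, 120 or 144 h; log-SD 0.4 or 0.6.

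**Worst case: the k slowest patients are lost from one arm only.** Ranges are over the six combinations of median and log-SD. Mean and median shifts use 20,000 simulated trials each, rejection rates 4,000.

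| k lost of 20 | Mean looks shorter by (h) | Median looks shorter by (h) | Mann-Whitney false-positive rate, observed only | Same, lost patients ranked worst |
|---|---|---|---|---|
| 0 | about 0 | about 0 | 4.2–5.3% | same |
| 1 | 5.3–15.6 | 2.2–5.6 | 5.7–6.0% | 3.7–5.1% |
| 2 | 9.3–26.0 | 4.5–10.7 | 8.1–9.1% | 3.4–4.4% |
| 4 | 15.7–41.8 | 9.0–20.5 | 16.3–17.6% | 3.1–3.7% |

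At k = 2, rejections with the depleted arm looking faster make up 7.2 to 8.4 percentage points of the 8.1 to 9.1%.

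**Losses unrelated to recovery.**
- Lost before anyone could be fit: the mean shifts by 0.3 h or less, which is simulation noise.
- Exit time spread evenly over 0 to 240 h for 2 patients of one arm (median 120 h, log-SD 0.5): about 1.1 of them lose their time on average, and the mean shifts by 1.5 h. With 1 such patient it shifts by 0.9 h.

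**Deaths unrelated to recovery speed, in one arm (median 120 h, log-SD 0.5).**
- 1 of 20: observed-only median 120.8 h; with the death ranked worst, 125.0 h.
- 2 of 20: observed-only median 121.9 h; with the deaths ranked worst, 130.5 h, a gap of 130.5 − 121.9 = 8.6 h. The arm without deaths has a median of 121.4 h, so the observed-only comparison shows almost no difference.

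**Chance that the rule is needed.** The probability of at least one such patient among 40 is 1 − (1 − q)^40. For assumed risks q of 1%, 2%, 5% and 10% this is 33%, 55%, 87% and 99%.

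**The case against.** The strongest reply is that missing data are left to the statistical analysis plan, which is not shown. That holds for the sensitivity analyses, and for them only. The sentence that defers them also fixes the main analysis on observed data, and the test is fixed too. A sensitivity analysis does not change which patients the main comparison contains. One could read the observed-data rule as covering the primary outcome alone, but then no rule is stated for this outcome, and the named tests still omit a patient without a value.

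Several stronger readings are tempting and should be resisted.

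- A reader might infer that the arm with more losses will look faster. The documents give no rate of death or post-operative withdrawal and do not say that those lost are the slowest. Patients are randomised at the preoperative clinic, so some withdrawals may precede surgery and say nothing about recovery.
- A reader might take the tabulated shifts as expected bias. They remove exactly the slowest patients from one arm only. For skewed times the plan points to Mann-Whitney and medians, where the shift is smaller. That worst ranks repair this scenario is close to built in, since the lost patients were the slowest already.
- A reader might infer that Mann-Whitney is the wrong test. It is acceptable once a death is given the worst rank; what is missing is the rule.
- A reader might treat this as the principal recovery endpoint. It is one of three items in the recovery profile, and the rationale names it last among several hoped-for benefits.

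Nor is a survival analysis free of assumptions: censoring withdrawals presumes that leaving is unrelated to recovery.

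**Conclusion.** The point stands in a limited form. The protocol itself fixes a comparison from which a patient who dies, or is withdrawn after surgery, before fitness is omitted. A death then does not count as a failure to recover.

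The consequence is conditional. It matters when the losses are deaths or relate to slow recovery, and it distorts the comparison when they differ between arms. In the constructed worst case, 2 losses of 20 in one arm roughly double the Mann-Whitney false-positive rate, to about 8 to 9%. Where up to 2 losses are unrelated to recovery, the effect is negligible. All times, spreads and loss risks are assumptions, because the protocol gives none.

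One secondary outcome is affected. The primary comparison of insulin resistance on the first post-operative day does not depend on it. The change is still worth making before the data are analysed by arm, because it costs almost nothing and one or two patients count in arms of 20.

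**What to change.** In Section 7.3, take time to surgical fitness out of the general sentence and give it its own rule. Keep every patient who has surgery in this comparison, in the randomised arm, where consent allows, and choose one of two analyses:

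1. Mann-Whitney, with death before fitness given the worst rank.
2. Kaplan-Meier curves with a log-rank test, with death treated as never reaching fitness: the patient stays in the risk set beyond the last observed fitness time and is not censored at death.

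Post-operative withdrawals may be censored at exit. Because that censoring may be informative, add a sensitivity analysis that gives them the worst rank. Report deaths and withdrawals before fitness by arm. The same sentence should say when the clock starts, since Section 5.4 gives the unit but not the origin.

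The cost is a change of wording. No new measurements are needed, only the time of death or withdrawal, which the patient notes should hold. The downside is that the result becomes a median, a rank-based effect or a hazard ratio instead of a mean difference in hours.

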## METHODS FOR ANY ADDITIONAL ANALYSES (EG, SUBGROUP AND ADJUSTED ANALYSES)

If differences are observed in baseline demographic and/or clinical variables prognostic of outcome, then the analysis of the primary and secondary outcomes will be adjusted for using regression-based analysis appropriate to the type of outcome variable. The trial statistician will describe details of sub-group analysis in the statistical analysis plan if possible.

DEFINITION OF ANALYSIS POPULATION RELATING TO PROTOCOL NON-ADHERENCE (E.G., AS RANDOMISED ANALYSIS), AND ANY STATISTICAL METHODS TO HANDLE MISSING DATA (EG, MULTIPLE IMPUTATION) All analysis will be performed according to the intention to treat principle. The primary analysis will be based only on data obtained; sensitivity analysis will explore sensitivity to assumptions around missing data and details will be included in the statistical analysis plan devised by the trial statistician.

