## 4. Introduction

## 4.1 Background and Rationale

The development of insulin resistance and hyperglycaemia following surgery is a well-documented phenomenon which is associated with increased morbidity and mortality.  Insulin sensitivity is reduced by approximately 50% following elective surgery and persists for at least five days postoperatively in the case of upper abdominal surgery. There is a dose-response relationship between the magnitude of surgery and the degree of insulin resistance postoperatively. In the case of colorectal surgery where the magnitude is variable the change is closely correlated with the duration of surgery. Blood loss is the other independent predictor of the degree of insulin resistance. Therefore this metabolic variable is governed by the degree of surgical trauma itself rather than any predisposing or associated factors.

It appears that endogenous glucose production (EGP) in the liver is unaffected by the suppressive effect of insulin per se, postoperatively. Thus the changes in insulin sensitivity following surgery are secondary to alterations in peripheral glucose uptake alone, and therefore reasonable to assume that the main site for this is skeletal muscle, being the largest organ involved.

The precise mechanism behind this loss of insulin sensitivity is unknown but it has been demonstrated that providing carbohydrates pre-operatively can attenuate this effect. Pre-operative carbohydrate drinks were also found to reduce pre-operative anxiety and hunger. There is also evidence that pre-operative carbohydrate drinks may decrease loss of post-operative muscle mass and function and attenuates protein catabolism. 6,8–11

In addition, receiving a carbohydrate drink 2 hours before the start of anaesthesia does not significantly affect the gastric residual volume compared to patients fasted overnight. 2,4,7,12

This practice, in conjunction with several other interventions, has now become routine with the introduction of Enhanced Recovery Protocols (ERP). These have been shown to reduce length of stay and complication rates for major surgery. A recent ERAS cohort study showed that patients that were treated with preoperative carbohydrates, experienced a 44% reduction in the risk of postoperative symptoms. 

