#### 5.6 Sample Size

The standard deviation for insulin resistance data was obtained from a previous study of pre-operative carbohydrate treatment in total hip replacement surgery (Soop 2001). Twenty patients in each group are needed based on 80% power for a two-sample t-test, detecting a minimal important difference of 15% in change of insulin resistance on the first postoperative day from baseline, with a standard deviation of 16% and a two-tailed significance level of 0.05. A minimal important difference of 25% was used in a previous study comparing pre-operative carbohydrate treatment with a placebo group for patients who had total hip replacement (Soop 2004) . In this study two carbohydrate drinks are being compared, PreLoad with Generation UCAN. Therefore, a smaller minimal important difference of 15% was deemed appropriate. This sample size calculation allows for 10% attrition.

\*\* Measured twice a day first three postoperative days then alternate days until discharge from hospital.

\*\*\*The baseline HOMA to be done on either of these 2 visits as long as the patient is fasted.

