## 10.2 BLOOD SAMPLING & HOMA CALCULATION OF INSULIN RESISTANCE

#### **BLOOD SAMPLING**

The HbA1C will be collected in an EDTA sample (both centres will analyse these samples using TOSOH HPLC analysers), 1.5mls blood for cortisol in a serum gel tube (both centres will analyse these samples with Advia Centaur analysers), insulin with 5-10ml of blood in a lithium heparin (orange) tube. The insulin samples need to be received in laboratory within 30 minutes, then centrifuged and frozen for transport to Central Manchester Foundation Trust laboratory in the case of Royal Blackburn Hospital. The Royal Surrey County Hospital will perform this test in-house. Both sites use Mercoda insulin ELISA kit. Serum Glucose samples will be collected in a yellow topped tube. Royal Blackburn Hospital uses an Ortho Vitros analyser and the Royal Surrey County Hospital uses Siemens Advia. However external proficiency testing data shows that on average the methods perform within 2.5% of each other, which is acceptable.

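### Covariate adjustment depends on observed baseline differences, and the protocol does not say whether the adjusted or the unadjusted result is primary; a fixed baseline-adjusted analysis would be cleaner and more powerful

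*Protocol*

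**What the plan says.** For the primary outcome, change in insulin resistance from baseline to postoperative day (POD) 1, section 7.3 names an unadjusted comparison: the groups "will be compared using either the Independent Samples T-Test or Mann-Whitney U Test", depending on skewness.

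The next part of 7.3, on additional analyses, makes adjustment conditional. Its sentence opens with the condition: "If differences are observed in baseline demographic and/or clinical variables prognostic of outcome, then the analysis of the primary and secondary outcomes". The method follows in the same sentence and is left general: the variables concerned "will be adjusted for using regression-based analysis appropriate to the type of outcome variable". It gives no list of covariates and no definition of a difference. It does not say which result is primary once the condition is met. On these lines, what it leaves to the SAP is subgroup detail: "The trial statistician will describe details of sub-group analysis in the statistical analysis plan if possible". Missing-data details are also deferred, in the paragraph that follows, but the adjustment rule is not.

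Section 5.6 sizes the trial on the unadjusted test, with "80% power for a two-sample t-test" and "a two-tailed significance level of 0.05".

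**The concern.** In a randomised trial, baseline differences between arms arise by chance. A rule that adjusts only when such differences are seen has three effects:

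- It lets the data choose the model, so the reported p-value and confidence interval come from a two-stage procedure rather than from either model alone.
- It gives up precision when a strong predictor happens to be balanced, because the predictor then stays out of the model although it would still reduce residual variance.
- It leaves two candidate answers, with the protocol silent on which one counts.

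With 20 patients per arm, chance imbalance is common and precision is scarce, so both the choice of model and the lost power matter.

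**Working it through.** **Inputs from the protocol (5.6).** Difference 15, SD of change 16, two-sided alpha 0.05, power 80%, 10% attrition, 20 per arm.

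**The plan's own figure.** n per arm = 2 × (1.960 + 0.842)² × 16² / 15² = 17.9, so 18. Allowing for attrition, 18 / 0.9 = 20. The stated sample size is reproduced. With 18 evaluable per arm, the exact power of the unadjusted t-test is 78%.

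**Assumptions not in the protocol.** Normal data; the t-test branch of 7.3; *difference* read as baseline p<0.05, baseline p<0.20, or a standardised difference above 0.25. R is the correlation of the covariate (multiple correlation if there are several) with the outcome.

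**How often chance alone fires the rule (18 per arm).**

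| Covariates | p<0.05 | p<0.20 | Std. difference >0.25 |
|---|---|---|---|
| 1 | 5% | 20% | 46% |
| 4 | 18–19% | 59% | 91% |

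**Simulated operating characteristics (one covariate, 18 per arm).** Entries for the triggered rule follow the same order of the three definitions.

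| R | Type I, triggered | Type I, better of the two results | Power, triggered | Power, fixed adjustment | Power, unadjusted |
|---|---|---|---|---|---|
| 0.3 | 4.8 / 4.6 / 4.6% | 6.4% | 78 / 79 / 79% | 81% | 78% |
| 0.5 | 4.4 / 3.9 / 3.8% | 7.4% | 79 / 81 / 83% | 88% | 78% |
| 0.7 | 3.6 / 2.7 / 3.0% | 8.3% | 80 / 84 / 89% | 96% | 78% |

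Fixed adjustment holds type I error at 4.8–5.1% in every setting run. Across all settings (one or four covariates, 18 or 20 per arm), the triggered rule gives 2.5–5.0%, and taking the better of the two results gives 6.4–8.5%.

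**Baseline HOMA as the covariate.** Let rho be the correlation between baseline and POD 1 values, with equal variances at the two times. The correlation of baseline with change has size √((1 − rho)/2), which is 0.59, 0.50 and 0.39 at rho = 0.3, 0.5 and 0.7. Baseline HOMA therefore falls inside the range of the table. The residual SD after adjustment is 16 × √((1 + rho)/2):

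- rho 0.3: 12.9; 15 / (12.9 × √(2/18)) = 3.49; power about 91%
- rho 0.5: 13.9; 15 / (13.9 × √(2/18)) = 3.24; power about 87%
- rho 0.7: 14.8; 15 / (14.8 × √(2/18)) = 3.04; power about 83%

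With baseline HOMA as the only possible trigger, the rule gives type I error of about 3.5–4.8% and power of about 78–85% over the same range of rho.

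**Where fixed adjustment does not help.** With four covariates that together reach only R = 0.3, fixed adjustment has 76% power against 78% unadjusted.

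**The case against.** **The rule sits under additional analyses.** On that reading the unadjusted test stays primary and its p-value is untouched. This is a fair reading. However, the sentence says that the analysis of the primary and secondary outcomes will itself be adjusted, which reads as replacement. The text does not settle the question, and that is part of the point.

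**Covariate lists are commonly SAP content.** This is true, and the absence of a list is not held against the protocol. The trigger itself is written in the protocol and is not deferred, so an SAP that follows the protocol would keep it.

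**Stronger claims that a reader might infer, and that do not hold:**

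- *The rule inflates false positives.* Followed as written, it is conservative. Inflation needs someone to choose the favourable result, which the protocol nowhere permits, although its silence on the primary result does not prevent it.
- *Adjustment is almost bound to be triggered.* The rule covers only variables prognostic of outcome, and the chance of firing runs from 5% to 91% with the definition and the number of covariates.
- *The protocol already names baseline HOMA and centre as predictors.* Section 4.1 names duration of surgery and says "Blood loss is the other independent predictor of the degree of insulin resistance"; both are measured after randomisation. The laboratory appendix notes that Blackburn's insulin samples go to another laboratory while "The Royal Surrey County Hospital will perform this test in-house". It also reports a common insulin kit and average glucose agreement within 2.5%, so it shows no centre effect. Baseline HOMA and centre are proposed here on design grounds.
- *Fixed adjustment always wins by a wide margin.* With weak covariates it does not. If several strong predictors could trigger adjustment, the triggered rule can rival a baseline-only model.

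**Conclusion.** The concern holds in a moderate form. The protocol fixes a data-dependent adjustment rule and leaves unclear which result is primary.

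The main cost is power. For baseline HOMA the loss against a fixed model is roughly 5 points at the low end of the ranges (78% against 83%) and 6 at the high end (85% against 91%). There is a mild departure from the nominal 5% in the conservative direction, and a risk of inflation to about 6.5–8% only under selective choice.

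These sizes rest on assumed correlations of 0.3–0.7, equal variances, normal data and 18 evaluable per arm; the protocol gives none of the correlations. The recommended model with centre added was not simulated separately. The stated sample size is not in error on this point.

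**What to change.** In 7.3, delete the condition on observed baseline differences. State that the primary analysis is an analysis of covariance of POD 1 insulin resistance (or its change from baseline), adjusted for baseline HOMA and centre regardless of observed balance. Report the unadjusted comparison as supportive. Adjust secondary outcomes in the same way, each for its own baseline where one is measured. Baseline tables remain descriptive.

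Baseline HOMA is already collected, at the assessment clinic or on the morning of surgery before the drink, and centre is known. Add planned resection type only if it is recorded before randomisation: the protocol lists a description of the operation taken from theatre or recovery-programme records, which is not shown to be the plan at randomisation, so a new field may be needed. Keep the list short. Leave operative duration and blood loss out of the primary model, because both are measured after randomisation.

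The cost is a sentence or two in the protocol, carried into the SAP, and one or two degrees of freedom. If the covariates prove only weakly prognostic, little is gained.
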